3.1.2. Treatment Groups

In this study, subjects will initially be given open-label DS-5565 15 mg QD. After treatment at this dose for 3 weeks (Visit 6, Week 3), subjects may be titrated to 15 mg BID based on efficacy and safety criteria as detailed in Section 5.1.1.

3.1.3. Study Endpoints

The primary endpoint is long-term safety based on assessment of treatment-emergent adverse events (TEAEs), clinical laboratory evaluations, physical examinations, electrocardiograms (ECGs), the Columbia-Suicide Severity Rating Scale (C-SSRS), and the Physician Withdrawal Checklist (PWC).

The secondary endpoints are:

- Changes from baseline to scheduled timepoint in ADPS and ADSIS
- Proportion of subjects with improvement in overall status at Week 52 as assessed by PGIC
- Changes from baseline to Week 52 in HADS depression and anxiety scores
- Changes in EQ-5D and SF-36 parameters from baseline to Week 52

3.1.4. Duration of the Study

The total duration of the study from First Subject Screened to Last Subject Last Visit is estimated to be approximately 39 months.

3.1.5. Duration of Subject Participation

For rollover subjects, the total study duration (for an individual subject's participation) will be approximately 56 weeks, including 52 weeks of open-label treatment and 4 weeks

of post-treatment follow-up. De novo subjects will also have a screening/baseline period of up to 3 weeks and therefore a total duration of approximately 59 weeks.

3.1.6. Stopping Rules

3.1.6.1. Stopping Rules for Individual Subjects

For any subject discontinued from the study based on one of the stopping rules outlined in Section 3.1.6.1.1 or 3.1.6.1.2, the associated event must be reported as an AE or SAE in the eCRF within 24 hours of awareness. Please refer to Section 9.4.1 for further instructions.

3.1.6.1.1. Elevations of Aminotransferases

Although a mechanism- or metabolism-based potential for drug-induced liver injury has not been established for DS-5565, instances of increased hepatic transaminases have been observed during the development program. In addition, acetaminophen, an agent known to cause liver injury (due to saturation of its metabolism when overdosed), is commonly used in this population and is included in this study as an allowed treatment for pain. As such, a standardized approach for stopping rules and careful monitoring of serum transaminases is considered prudent. Stopping rules for elevation in serum transaminases are included as a general precaution, with attention to Food and Drug Administration (FDA) guidance for detection and assessment of drug-induced liver injury premarketing clinical evaluations and are described below. Specific recommendations regarding monitoring of subjects with elevations are described in Section 9.2.2.

Subjects with any of the following elevations in aminotransferases should be discontinued from treatment and followed closely as noted above.

- Increase in alanine aminotransferase (ALT) or aspartate aminotransferase (AST) ≥ 5 x upper limit of normal (ULN)
- ALT or AST rises to ≥ 3 x ULN and persists for more than 2 weeks
- Concurrent increases in ALT or AST ≥ 3 x ULN and total bilirubin ≥ 2 x ULN
- ALT or AST ≥ 3 x ULN associated with a clinical presentation suggestive of liver injury (i.e. including the appearance of fatigue, nausea, vomiting, right upper quadrant pain or tenderness, fever, rash, and/or eosinophilia)

A flow diagram displaying the criteria for discontinuing treatment based on aminotransferase elevations is provided in [Appendix 17.1](#).

3.1.6.1.2. Suicidal Behavior and Ideation

The $\alpha_2\delta$ ligand class of medications has been associated with increased risk of suicidal thoughts or behavior (Section 9.2.1). Two separate cases of completed suicide were observed in the Phase 2 DS5565-A-J202 study.

The C-SSRS and Mini-international Neuropsychiatric Interview (MINI) (Version 6.0) are to be administered at any time during the study (including unscheduled visits) where the investigator/study coordinator/site staff recognizes or become aware of (and this includes

if this awareness arises during unscheduled visits or non-face-to-face communications with the patient or his/her family):

- Any suggestion of mood disturbance and/or any awareness of a potential suicidal risk,
- Substantial changes in their psychosocial environment (ie, the death of or separation of close family/friend, sudden financial burden, worsening of medical condition, etc); in this case administration of the C-SSRS/MINI and consultation with a psychiatrist (onsite preferably) should be performed.

In this study, the C-SSRS will be administered at all clinic visits. Based on the C-SSRS and investigator judgment, if a subject is identified as being at risk for suicide, appropriate safety measures should be implemented, including:

- A subject should be discontinued from the study and immediately referred to a mental health professional for further evaluation if subjects have a YES response to any question on the C-SSRS at any visit (current or past), unless the subject falls into the “Possible Exception” category below:
 - Possible exception (applying to YES responses to C-SSRS Q1 and/or Q2 only):
 1. The benefit from continuation on the study medication significantly outweighs the risk of continuing the patient on study drug. Such cases need to be discussed with the sponsor medical director and should take into account the mental health professional evaluation AND
 2. The justification for continuing the subject in the study under these circumstances is to be appropriately documented per study procedure

Subjects should be discontinued from the clinical study and immediately referred to a mental health professional (preferably an onsite psychiatrist evaluation if possible) if subjects are assessed as having current severe or uncontrolled major depressive disorder or anxiety disorders by the MINI at any visit (current or past) and if any of the following conditions apply:

- The investigator determines that there is a suicidality risk, irrespective of any scales or
- Any “Yes” response to:
 - MINI questions
 - Module A (Major Depressive Disorder) question A3, G or
 - Any question on Module B (Suicidality) or
 - Relevant C-SSRS questions, with discontinuation criteria as outlined above.

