4.1.2. Exclusion Criteria

All Subjects

1. Clinically significant unstable neurologic, psychiatric, ophthalmologic, hepatobiliary, respiratory, or hematologic illness or unstable cardiovascular disease (e.g. severe hypotension, uncontrolled cardiac arrhythmia, or myocardial infarction) or any other concurrent disease during the preceding study (for rollover subjects) or within 12 months prior to screening (for de novo subjects) that in the opinion of the investigator would interfere with study participation or assessment of safety and tolerability
2. Subjects who are at risk of suicide as defined by their responses to the C-SSRS or in the opinion of the investigator. Note: Subjects answering "yes" to any of the questions about active suicidal ideation/intent/behaviors occurring within the past 12 months must be excluded (C-SSRS Suicide Ideation section – Questions 3, 4, or 5; C-SSRS Suicidal Behavior section, any of the suicide behaviors questions). Such subjects should be referred immediately to a mental health professional for appropriate evaluation.

3. Subjects who are unlikely to comply with the protocol (e.g. uncooperative attitude, inability to return for subsequent visits) and/or otherwise considered by the investigator to be unlikely to complete the study
4. Subjects with severe or uncontrolled depression that, in the judgment of the investigator, makes the subject inappropriate for entry into the study
5. Subjects with pain due to other conditions (e.g. DPNP or post-herpetic neuralgia) that, in the opinion of the investigator, would confound assessment or self-evaluation of the pain associated with FM
6. Subjects with pain due to any widespread inflammatory musculoskeletal disorder (e.g. rheumatoid arthritis, lupus) or widespread rheumatic disease other than FM.
7. Abuse or dependence of prescription medications, street drugs, or alcohol within the last 1 year
8. Any history of a malignancy other than basal cell carcinoma within the past 5 years
9. A diagnosis of untreated sleep apnea or initiation of treatment for sleep apnea within the past 3 months
10. Known hypersensitivity to $\alpha_2\delta$ ligands or other components of the study medications
11. Pregnancy or breast-feeding, or intent to become pregnant during the study period

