12. Abnormal investigative tests (i.e. ECGs) and laboratory values judged by the investigator to be clinically significant at the End-of-Treatment visit (Visit 11, Week 13) in the preceding study (for rollover subjects) or at screening (for de novo subjects), with particular focus on:
 - Abnormal renal function defined as calculated CrCl < 60 mL/min determined by the central laboratory using the Cockcroft-Gault equation,⁴ blood urea nitrogen > 1.5 × ULN; serum creatinine > 1.6 mg/dL (> 141.4 μmol/L); or
 - Abnormal liver function defined as AST (SGOT) > 2.0 × ULN, ALT (SGPT) > 2.0 × ULN; alkaline phosphatase > 1.5 × ULN; total bilirubin > 1.2 × ULN. If a subject has total bilirubin > 1.2 ULN, unconjugated and conjugated bilirubin fractions should be analyzed and only subjects documented to have Gilbert's syndrome may be enrolled; or
 - Creatine kinase > 3.0 × ULN

For De Novo Subjects Only

13. Unable to undergo pre-study washout of prohibited concomitant medications (as listed in Section 5.2.1 of the protocol)
14. Current severe or uncontrolled major depressive disorder or anxiety disorders as assessed by the Mini-international Neuropsychiatric Interview (MINI) interview (Version 6.0) at screening are excluded, but mild to moderate major depression or

anxiety disorders are permitted provided that the investigator assesses the patient as clinically stable and appropriate for entry into the study

15. Any diagnosis of lifetime bipolar disorder or psychotic disorder
16. Subject is currently enrolled in or has not yet completed at least 30 days since ending another investigational device or drug study or is receiving other investigational agents
17. Subject is an employee of the study center, an immediate family member* of an employee of the study center, or an employee of Daiichi Sankyo, INC Research, or any of the study vendors supporting this study. *(spouse, parent, child, or sibling, whether biological or legally adopted)

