4.2. Removal of Subjects From Therapy

Data from all enrolled subjects are important to achieve study objectives, and subjects should be encouraged to adhere to protocol instructions and visit schedules. However, in accordance with the Declaration of Helsinki and other applicable regulations, a subject has the right to withdraw from the study at any time, and for any reason, without

prejudice to his or her future medical care by the study physician or at the study site. The investigator is also free to terminate a subject's involvement in the study at any time if the subject's clinical condition warrants such action. The sponsor or regulatory authorities also may request termination of the study at any time due to safety issues or concerns related to study conduct.

NOTE: In this study, the C-SSRS will be administered at all clinic visits. Based on the C-SSRS and investigator judgment, if a subject is identified as being at risk for suicide, appropriate safety measures should be implemented (see Section 3.1.6.1.2).

The MINI and C-SSRS are to be administered at any time during the study (including unscheduled visits) based on investigator's discretion (Section 3.1.6.1.2).

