9.2.1. Suicidal Behavior and Ideation

An FDA-conducted pooled analysis of placebo-controlled clinical studies of antiepileptic drugs with varying mechanisms of actions and indications, including pregabalin and gabapentin, showed an increased risk of suicidal thoughts or behavior in subjects receiving these drugs.¹¹

The C-SSRS and MINI are to be administered at any time during the study (including unscheduled visits) where the investigator/study coordinator/site staff recognizes or become aware of (and this includes if this awareness arises during unscheduled visits or non-face-to-face communications with the patient or his/her family):

- Any suggestion of mood disturbance and/or any awareness of a potential suicidal risk,
- Substantial changes in their psychosocial environment (ie, the death of or separation of close family/friend, sudden financial burden, worsening of medical condition, etc); in this case administration of the C-SSRS/MINI and consultation with a psychiatrist (onsite preferably) should be performed.

The C-SSRS will be administered at baseline and at every clinical assessment thereafter. Based on the C-SSRS and investigator judgment, if a subject is identified as being at risk for suicide, appropriate safety measures should be implemented, including:

- A subject should be discontinued from the study, and immediately referred to a mental health professional for further evaluation, if a 'YES' response has been recorded for any question on the C-SSRS at any visit (current or past), unless the subject falls into the 'Possible Exception' category below:
 - Possible exception (applying to yes responses to C-SSRS Q1 and/or 2 only):
 1. The benefit from continuation on the study medication significantly outweighs the risk of continuing the subject on study drug. Such cases need to be discussed with the sponsor medical director and should take into account the mental health professional evaluation AND
 2. The justification for continuing the subject in the study under these circumstances is to be appropriately documented per study procedure.

Subjects should be discontinued from the clinical study and immediately referred to a mental health professional (preferably an onsite psychiatrist evaluation if possible) if subjects are assessed as having current severe or uncontrolled major depressive disorder or anxiety disorders by the MINI at any visit (current or past) and if any of the following conditions apply:

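### The MINI stopping rule, read literally, requires a stop for investigator-judged suicidality risk only when a severe or uncontrolled MINI diagnosis is also present

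*Combined protocol and SAP*

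**What the plan says.** Section 3.1.6.1.2 contains two stopping rules for suicidality.

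- **C-SSRS rule.** Any YES leads to discontinuation and immediate referral, apart from one carve-out: "Possible exception (applying to YES responses to C-SSRS Q1 and/or Q2 only"). The carve-out needs a benefit that clearly exceeds the risk, a mental health evaluation, discussion with the sponsor's medical director and a documented justification.
- **MINI rule.** A current severe or uncontrolled major depressive or anxiety disorder on the MINI is joined to a list by the words "disorders by the MINI at any visit (current or past) and if any of the following conditions apply". The first item on the list reads "The investigator determines that there is a suicidality risk, irrespective of any scales or". The others are a Yes on the named MINI Module A question or on any Module B question, and the relevant C-SSRS questions.

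Section 9.2.1 repeats the MINI rule with the same connective: "by the MINI at any visit (current or past) and if any of the following conditions apply".

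Investigator judgment also appears in the sentence that introduces the C-SSRS rule: "if a subject is identified as being at risk for suicide, appropriate safety measures should be implemented". Section 4.2 adds a general permission: "The investigator is also free to terminate" a subject's involvement when the clinical condition warrants it.

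Under Sections 3.1.6.1 and 9.4.1, an event that meets an individual stopping rule must be reported in the eCRF within 24 hours.

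**The concern.** A judgment that is meant to hold whatever the scales show has been placed under a precondition that is itself a scale result. A site that follows the text word by word would conclude that the investigator's determination does not by itself require discontinuation. A site that follows the evident sense would conclude that it does. A stopping rule should not allow both answers.

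The subject matter makes this worth fixing. Section 3.1.6.1.2 records two completed suicides in a Phase 2 study of this drug, and long-term safety is the primary objective. Two things depend on whether the rule is met: whether the stop is required or left to discretion, and whether a non-serious event must be reported within 24 hours.

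**Working it through.** No arithmetic figure in the plan is at issue. The check is a truth table for the rule, followed by a search for any other place that supplies the stop.

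**Inputs (Section 3.1.6.1.2, repeated in 9.2.1)**

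- M: current severe or uncontrolled major depressive or anxiety disorder on the MINI.
- I: investigator determines a suicidality risk.
- Q: Yes on the named MINI Module A question or on any Module B question.
- C: a C-SSRS YES that is not exempted under the item 1 and 2 carve-out.

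**Rule as literally written**

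Stop = C or [M and (I or Q or C)].

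**Rule with the investigator's determination standing alone**

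Stop = I or C or [M and (Q or C)].

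**All eight combinations with I true**

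| M | C | Q | Stop as written | Stop with I stand-alone |
|---|---|---|---|---|
| yes | yes | yes | yes | yes |
| yes | yes | no | yes | yes |
| yes | no | yes | yes | yes |
| yes | no | no | yes | yes |
| no | yes | yes | yes, through the C-SSRS rule | yes |
| no | yes | no | yes, through the C-SSRS rule | yes |
| no | no | yes | **no** | yes |
| no | no | no | **no** | yes |

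As written, 6 of 8 combinations stop: 4 through M and 2 through the separate C-SSRS rule. The 2 that do not stop share one description: no severe or uncontrolled MINI diagnosis and no non-exempted C-SSRS YES. The table describes scope. It is not a frequency.

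**Does another section supply the missing stop?**

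- Section 3.1.6.1.2, introduction to the C-SSRS rule: calls for safety measures. The discontinuation bullet beneath it needs a C-SSRS YES.
- Section 3.1.6.1.2, unscheduled assessments: awareness of a potential risk requires the C-SSRS and MINI to be given. It does not itself require a stop.
- Section 6.3: the check of continued eligibility refers back to 9.2.1, which has the same wording.
- Section 4.2: permits withdrawal and does not require it.
- Section 4.1.2, Exclusion 2: "Subjects who are at risk of suicide as defined by their responses to the C-SSRS or in the opinion of the investigator". Opinion alone is enough here, but this governs entry only.

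None supplies it.

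**Is the combination reachable?** Yes. For de novo subjects, Exclusion 14 says that severe or uncontrolled disorders "at screening are excluded, but mild to moderate major depression or" anxiety disorders are permitted if the subject is clinically stable. A subject who stays in that range never meets M.

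**Reporting.** Section 9.4.1 names three kinds of event for the 24-hour report: SAEs, combined hepatic abnormalities, and events that meet an individual stopping rule. In the two uncovered rows the third does not apply, so the report is required only if the event is an SAE.

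**The case against.** The strongest reply is that the text can be read the other way. The connective repeats the word if, which allows separate triggers. The first item disclaims reliance on scales. The C-SSRS item adds nothing under a conjunction, because a C-SSRS YES already stops the subject, but it makes sense as a cross-reference in a list of separate triggers. This stands as evidence of intent and is why the point is a probable drafting error. It does not repair the text, since no section states the separate trigger.

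Second, the person who judges the risk also controls the stop. Harm would need an investigator who finds a suicidality risk and still keeps the subject on drug. That keeps the gap small, but permission is not a requirement, and the 24-hour report follows the stopping rule.

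Third, a subject with an exempted YES on C-SSRS item 1 or 2 has already been through evaluation and sponsor discussion. This stands, and is a reason to leave it to the sponsor how that process and the new criterion interact.

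Fourth, entry and on-treatment criteria may properly differ. This stands too: Exclusion 2 is a contrast, not proof of error.

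A reader might go further in three ways that the documents do not support:

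- That at-risk subjects are unprotected. Section 3.1.6.1.2 calls for safety measures and for both scales on any awareness of potential risk, and any non-exempted C-SSRS YES stops treatment.
- That the diagnosis half of the rule cannot be met on treatment, because the MINI is scheduled only at de novo screening. The unscheduled MINI is required in exactly the situation at issue.
- That discretionary withdrawals would escape safety review. The DSMB's remit in Section 11.9 covers any emerging safety or tolerability issue. Section 4.2.1 offers an adverse-event code after start of treatment and requires a reason under its residual category.

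**Conclusion.** The point holds on the literal text of both sections. The investigator's determination of suicidality risk is a required stop only with a severe or uncontrolled MINI diagnosis, contrary to the criterion's own terms. The consequence is limited to subjects judged at risk who have no such diagnosis and no C-SSRS YES other than an exempted one on item 1 or 2. For them the stop is discretionary, and a non-serious event carries no 24-hour report.

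The conclusion rests on the literal reading. It also takes M as absent at every visit that counts. The rule covers current and past visits, and the documents do not say whether a MINI from the preceding study counts for rollover subjects. How often the combination would occur cannot be derived from the documents. This is a small gap that should be closed because the risk is grave and the repair is simple.

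**What to change.** In both 3.1.6.1.2 and 9.2.1, take the investigator's determination of suicidality risk out of the list under the MINI diagnosis. Make it a stand-alone criterion for discontinuation, with immediate referral to a mental health professional and the 24-hour report of Sections 3.1.6.1 and 9.4.1.

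The sponsor should also state two things, both clinical choices that this repair does not settle:

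- whether a Yes on the listed MINI questions (Module A or Module B) is a separate trigger or needs the diagnosis as well;
- how the C-SSRS item 1 and 2 exception process interacts with the new criterion.

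The drafting cost is one criterion moved in two sections and a notice to sites. The clinical cost is possibly a few extra discontinuations, and Section 1.3 lists abrupt discontinuation as a class caution. The withdrawal checklist at Day 3 and Week 2 of follow-up covers early discontinuers, but it detects withdrawal symptoms and does not prevent them.

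The effect on the goal of about 500 subjects with 52 weeks of exposure (Section 11.11) depends on an unknown rate. If the criterion stopped an assumed extra fraction p of would-be completers, the additional would-be completers needed are 500/(1 − p) − 500:

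- p = 0.1%: 0.5
- p = 0.5%: 2.5
- p = 1%: 5.1
- p = 2%: 10.2

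Against 2100 to 2500 anticipated double-blind completers eligible to roll over, this is minor across the assumed range.

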3.1.6.2. Stopping Rules for the Study

Circumstances under which the study may be stopped based upon independent Data and Safety Monitoring Board (DSMB) recommendation are specified in Section 11.9. In addition, the study may be terminated at any time at the sponsor's discretion.

